- Participants that require hospitalization due to effect of study drugs will continued to be monitored for safety but the data will not be included in the final analysis. The study enrollment will stop prematurely if two or more participants require hospitalization.
- Participants in the standard of care arm will be withdrawn if they develop severe adverse reactions from the study medication that prevent continued compliance. If participants in the standard treatment arm have 25(OH)D levels >100ng/mL they will be reduced to taking 2,000IU daily but will not automatically be removed from the study.
- We will recommend that participants who withdraw from the study get a BMP and Vitamin D level drawn within 3 months of withdrawing to ensure no negative effects on their renal function or calcium level and to ensure that they are being treated for vitamin D deficiency.

XV. RISKS TO PARTICIPANTS

- The major risk to human subjects is related to symptomatic hypercalcemia from vitamin D toxicity.
 - These symptoms typically occur at serum 25(OH)D levels >150ng/mL
 - The risk is greater with prolonged high dose vitamin D administration (Kaur).
 - Symptoms of vitamin D toxicity include fatigue, muscle weakness, anorexia, dehydration leading to acute kidney injury, polyuria and polydipsia, confusion, and gastrointestinal effects such as constipation, nausea/vomiting.
 - The risk of vitamin D toxicity is greatest 1 week after administration of the high-dose bolus but the overall risk remains low (Kearns).
 - Large bolus vitamin D administration has been incompletely studied so there are possible unforeseen risks associated with this.
- Participants will undergo blood draws at the initial visit and every three months. When done by persons trained in phlebotomy there is minimal risk. The risks are unlikely but do include unintentional bleeding, bruising, hematoma, or infection. There is also risk of vasovagal events.

XVI. MANAGEMENT OF RISKS

- Overall, the risk of vitamin D toxicity remains very low (Kearns). We will monitor vitamin D and calcium levels one week after starting the study medications. We will also monitor calcium levels every three months.
 - If participants do develop symptoms listed above, treatment of the hypercalcemia will be managed outpatient by the investigators or other provider at PAMC. If symptoms become so severe that they require hospitalization, they will be admitted to Parkview Medical Center and managed by the inpatient IM residents.
- Blood draws will all be done by phlebotomy trained individuals with standard precautions. The site will be clean prior to the blood draw. Direct pressure and bandage will be used after the blood draw. Participants will be asked prior to the blood draw if they have had vasovagal episodes before and if they would like to lay down while having their blood drawn.

XVII. POTENTIAL BENEFITS

- Vitamin D deficiency has historically been associated with bone disorders but research in recent years has shown to play a role in disease states of multiple body systems. Treatment of vitamin D deficiency has been shown to resolve symptoms related to deficiency as well as reduce risk of developing certain health conditions.
- Single, large-bolus treatment also reduces the daily burden of traditional supplementation.
- Results from this study could potentially influence clinical practices for the treatment of vitamin D deficiency.

XVIII. PROVISIONS TO MONITOR THE DATA FOR SAFETY OF PARTICIPANTS

- Data will be evaluated at a minimum of once every month to ensure safety of all participants. It will likely be reviewed more frequently than this and on an individual basis for each participant as they have their routine blood draws.

- The investigators or study coordinator will identify, document, and report any adverse events.
- The summarized safety data will be reviewed every three months by the primary investigator.

XIX. PROVISIONS TO PROTECT THE PRIVACY INTEREST OF PARTICIPANTS

- We do not anticipate any impact of the study or study procedures on the participants' privacy interests. All study meetings and lab draws will take part at facilities frequented by all patients of the Parkview Adult Medicine Clinic.

XX. MEDICAL CARE AND COMPENSATION FOR INJURY

- The risk of injury due to participation in this study is exceedingly low. If injury dose occur, participants will be cared for at the Parkview Adult Medicine Clinic. If hospitalization is necessary, participants will be admitted to the Parkview Internal Medicine Residency inpatient teams.
- Participants requiring medical attention due to the study medications will not be compensated monetarily but will also not have to pay for the medical care they receive that is specifically tied to the study.
- The administration at Parkview Medical Center as agreed to cover the cost for patients that require hospital admission due to study participation. Please see Appendix F for approval letter from administration.

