High dose Vitamin D therapy in children and adolescents, also known as Stoss therapy, was initiated in late 1930's Germany in the study of treatment and prevention of rickets (13). Since that time several studies have been performed to investigate Vitamin D supplementation in many different areas, patient populations and disease states. Current Endocrine Society guidelines define vitamin D deficiency at levels <20 ng/mL and insufficiency of Vitamin D at levels <30 ng/ml. Those guidelines recommend daily supplementation equivalent to 5,000-6,000 IU to achieve levels above this range (2). There are not guidelines regarding the frequency of checking Vitamin D levels while on treatment.

The significance of this research will aim to help guide treatment guidelines in terms of routine laboratory testing for follow-up, which will then potentially aid in guidance of when repeat dosing will occur. Upon review of the literature, many articles looked at serum levels immediately after large dose administration and with follow up as far as 9 months, but in the longer follow up studies laboratory testing from initial dose to last check was sparse. While many studies had short term follow up after initial dose, whether this was due to initial serum Vitamin D levels or dosage administered was not clearly defined. This study will aim to provide closer follow-up after a researched dose of 300,000IU that has been shown to have minimal adverse effects and multiple benefits beyond serum Vitamin D levels.

III. **PRELIMINARY STUDIES**

The pharmacodynamics of cholecalciferol allow for the potential of infrequent, large bolus administration. Once absorbed, cholecalciferol is either metabolized into 25(OH)-D or can be redistributed into fat. 25(OH)-D has a prolonged circulating half-life of approximately 2-3 weeks prior to being further hydroxylated in the kidney to the active metabolite (14). Cholecalciferol that is redistributed into fat is released slowly overtime to sustain circulating levels of 25(OH)-D for prolonged periods of time between dosing (13, 15, 16).

To this point, there has been inconclusive research on the efficacy of high dose vitamin D supplementation for vitamin D deficiency. Studies have shown that doses of 300,000IU are typically most efficacious for normalizing vitamin D levels while minimizing adverse effects (16). Dosage of 250,000IU or less have been ineffective for long-term improvement of vitamin D status (17, 18, 16).

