Doses greater than 300,000IU have shown similar efficacy in raising serum vitamin D levels but increase the risk of adverse effects (19). No studies have identified a standard duration of efficacy for large bolus vitamin D supplementation.

Of the studies that were reviewed, none showed significant adverse effects related to hypervitaminosis D. This was even with cholecalciferol doses greater than 300,000IU (13, 15, 16). Two case series that evaluated patients with vitamin D toxicity in India showed toxicity resulting from repeated cholecalciferol administration totaling greater than 1,000,000IU over a minimum of three months. All case reports of hypervitaminosis D reviewed had a significantly higher dose of cholecalciferol than our proposed dose.

IV. RESEARCH STUDY DESIGN

- Study will be a prospective, unblinded, randomized controlled study.
- There will be two study arms:
 - Large-bolus group that will get one-time, 300,000IU cholecalciferol.
 - Standard treatment group that will take 5,000IU cholecalciferol daily.
- Participants will be randomized based on the order they join the study. *Randomizer.org* was used to create a randomly organized set of 20 including 10 ones (large bolus) and 10 twos (standard treatment).

	A	B	C	D
1	Research Randomizer Results:			
2	2 Sets of 10 No Numbers Per Set			
3	Range: From 1 to 2 -- No			
4	Set 1	Set 2		
5	2	2		
6	1	1		
7	2	1		
8	1	2		
9	2	1		
10	2	2		
11	1	1		
12	1	2		
13	1	1		
14	2	2		
15				

- | | | | |
|-----|----------|-----|----------|
| 1. | Bolus | 11. | Standard |
| 2. | Standard | 12. | Bolus |
| 3. | Bolus | 13. | Standard |
| 4. | Bolus | 14. | Standard |
| 5. | Standard | 15. | Bolus |
| 6. | Standard | 16. | Standard |
| 7. | Bolus | 17. | Bolus |
| 8. | Bolus | 18. | Standard |
| 9. | Bolus | 19. | Bolus |
| 10. | Standard | 20. | Standard |

We will repeat this organization for subsequent sets of 20 participants to maintain relatively equal groups as participants are added.

- We plan to enroll a total of 100 participants. We should be able to meet the goals of the study with 86 participants. Please see Appendix A for calculation of study size.
- We expect the study to last a total of 20 months:
 - 6 months for initial enrollment
 - 12 months for data gathering
 - 2 months for analysis and write up

V. ABOUT THE SUBJECTS

- We plan to enroll a total of 100 participants.
- We anticipate 86 participants will complete the study.

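### Section XIV drops randomised participants hospitalised because of study drug from the final analysis: a post-randomisation exclusion triggered by a treatment effect and open to judgement with the arm known

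*Protocol*

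**What the plan says.** Section XIV (Withdrawal of Participants) deals with admissions caused by the study medication. Such participants, it says, "due to effect of study drugs will continued to be monitored for safety but the data will not be included in the final analysis". The clause sets no time limit and does not say which data it means.

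These places bear on it:

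- Section IV: "Study will be a prospective, unblinded, randomized controlled study".
- Section XI: the prescription depends on the randomised group, so randomisation precedes any dose.
- Section XV, on timing: "The risk of vitamin D toxicity is greatest 1 week after administration of the high-dose bolus but the overall risk remains low". On the link to the measured variable: "These symptoms typically occur at serum 25(OH)D levels >150ng/mL".
- Section XIV, for a standard-arm participant whose 25(OH)D exceeds 100 ng/mL: this person "will be reduced to taking 2,000IU daily but will not automatically be removed from the study".
- Section XVIII: "The investigators or study coordinator will identify, document, and report any adverse events", and "The summarized safety data will be reviewed every three months by the primary investigator".

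The Protocol names no intention-to-treat or other analysis set that would bring the hospitalised participants back.

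**The concern.** Randomisation makes the arms comparable only if those randomised stay in the comparison, or leave it for reasons unrelated to treatment. Here the reason for leaving is an effect of treatment. Section XV ties toxicity symptoms to high 25(OH)D, which is the variable the trial compares, and puts the risk highest in the week after the bolus. The exclusion can therefore fall unequally on the arms and be related to the measured level.

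Whether a participant stays in can also turn on attribution alone. An admission of 10 days or less for an unrelated illness triggers no withdrawal under Section XIV. The same short admission, if attributed to study drug, removes the data. The Protocol does not say who makes that call and describes no blinded or independent adjudication. That the arm would be known is an inference from the open design, but a direct one.

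Two things are at stake: the unbiasedness of the between-arm comparison of 25(OH)D and, if the final analysis includes safety results, whether the most severe toxicity cases appear in them.

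**Working it through.** **1. The plan's own figures.** Appendix A gives SD 6.7, margin of error 3, z = 1.96 and 1.282, a 6-unit difference and 90% retention.

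- Confidence interval: 2 × (1.96 × 6.7 / 3)² = 38.32 per arm; × 2 = 76.64; / 0.9 = 85.16 (stated 85).
- Power, with 6 as the difference: 2 × (3.242 / (6/6.7))² = 26.21 per arm; × 2 = 52.42; / 0.9 = 58.25 (stated 58).

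Both reproduce. The exclusion rule does not enter them, so correcting it changes no sample size.

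**2. Shift in an arm mean.** Let one participant in an arm of n differ from the mean of the others by d. The full arm mean is the mean of the others plus d/n, so exclusion moves it by −d/n. The arm size is 86/2 = 43 (expected completers, Sections IV and V) or 100/2 = 50 (enrolled). The values of d are assumptions: the Protocol gives no expected 1-week level. The largest sets 150 ng/mL, Section XV's symptom threshold, against an assumed mean of 50.

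| n | d (ng/mL) | Shift on exclusion (ng/mL) |
|---|---|---|
| 43 | +100 (150 vs 50) | −2.3 |
| 50 | +100 | −2.0 |
| 43 | +50 (100 vs 50) | −1.2 |
| 43 | −10 (assumed, after treatment is stopped) | +0.2 |

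Two exclusions at d = +100 give 2 × 100/43 = 4.7 ng/mL. The Section XIV rule on two or more hospitalisations stops enrolment only. It does not cap exclusions among those already enrolled.

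**3. Later visits.** Section III states that "25(OH)-D has a prolonged circulating half-life of approximately 2-3 weeks". Let the 100 ng/mL excess at week 1 decay at that rate:

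- 3 months, 12 weeks later: 100 × 0.5^(12/2) = 1.6 and 100 × 0.5^(12/3) = 6.3 ng/mL. Divided by 43, the shift is 0.04 to 0.15.
- 9 months, 38 weeks later, at the slower rate: 100 × 0.5^(38/3) = 0.015 ng/mL. Divided by 43, the shift is about 0.0004.

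The slow release from fat described in the same section would make these figures larger.

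**4. Safety, only if the final analysis includes it.** One drug-related admission among 50 bolus participants is 2.0% (exact 95% CI 0.05 to 10.6%). With that person removed it reads 0 of 49, or 0% (0 to 7.3%).

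**The case against.** The strongest reply is that this will hardly matter. The Protocol calls the toxicity risk low, so there may be no cases at all. The 2.3 ng/mL figure needs a participant 100 ng/mL above the rest, about 15 times Appendix A's SD (100/6.7), and it applies at week 1. Appendix A takes its power difference from 9 months, where the calculated shift is negligible. In that example exclusion also lowers the bolus mean, so it works against a non-inferiority claim. All of this is right and limits the size. It does not make the rule sound: Section XV itself says large bolus dosing is incompletely studied, and the sign can reverse.

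Second, the data left out may mean only those from the continued monitoring after admission. That reading is possible. The clause does not say so, and even then collected post-randomisation values would be discarded because of a treatment effect.

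Third, the sentence separates safety monitoring from the final analysis, and Section XVIII keeps adverse event reporting and three-monthly summaries going. On that reading the safety results are untouched, so the 1/50 versus 0/49 contrast is conditional and should not drive the grading.

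Fourth, the trigger is an attributed admission, not the 25(OH)D result itself. That is correct: the link to the outcome is indirect, through toxicity. The rule for levels above 100 ng/mL is also no contradiction, since it concerns continued participation and not analysis. The same section withdraws standard-arm participants whose severe reactions prevent compliance. The contrast shows only that Section XIV does not treat a high level as a reason for automatic removal.

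**Conclusion.** The point holds and should be fixed. The Protocol states a rule that removes randomised participants from the final analysis because of an effect of treatment, with attribution open to knowledge of the arm, and no other section corrects it. It is a positive instruction, not a detail left to an analysis plan.

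The likely size is small. For one excluded bolus participant it is about 1 to 2 ng/mL at week 1 under the assumed high values, 0.04 to 0.15 at 3 months and essentially nil at 9 months on the stated half-life. Appendix A's 3-unit margin gives a sense of scale and is not a threshold for this bias. The net direction is unknown. The safety consequence exists only under the wider reading of the final analysis. These figures rest on the assumed deviations, 43 to 50 per arm and simple exponential decay. The defect itself rests on none of them.

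**What to change.** In Section XIV, delete the clause that leaves these data out of the final analysis. In its place state that:

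- participants hospitalised because of study drug are analysed in their assigned arm with all 25(OH)D and calcium values actually collected, before and after the admission;
- drug-related hospitalisations are reported by arm over all randomised participants (a denominator of those who took study drug would also be acceptable, if named in advance);
- any analysis that excludes these participants is supportive only.

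The cost is one clause deleted and a short statement added. It requires no new visits or tests and no change in sample size, and it leaves clinical management as it is. The drawback is a little extra variability from partial or off-treatment values.

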Appendix A: Confidence interval and sample size calculations

For Confidence interval of 95%

- 85 participants (rounded to nearest integer)

For Power of 90%

- 58 participants

Assumptions:

- Acceptable error rate of 3 units
- Significant data meaning > 6 unit change from baseline
- Standard deviation on 6.7
- The latter 2 were taken from Premaor et al.

Calculation for Confidence interval:

$$n_i = 2 \left(\frac{Z\sigma}{E} \right)^2 :$$

N = sample size

Z = constant for desired confidence interval = 1.96

σ is the standard deviation of the outcome of interest = 6.7

E = acceptable margin of error = 3

This was then multiplied by 2 (for the treatment group vs control group) and then divided by .9 (assuming a 90% retention rate)

Calculation for Power:

$$n_i = 2 \left(\frac{Z_{1-\alpha/2} + Z_{1-\beta}}{ES} \right)^2$$

N = sample size

$Z_{1-\alpha/2}$ = constant for standard normal distribution of 1-alpha/2= 1.96

$Z_{1-\beta}$ = constant for standard normal distribution of 1-beta= 1.282 (if power of 90%)

$$ES = \frac{|\mu_1 - \mu_0|}{\sigma}$$

ES = Effect Size =

Numerator is the expected difference between populations (taken from 9 month difference of Premaor et al)

σ is the standard deviation of the outcome of interest = 6.7

This was then multiplied by 2 (for the treatment group vs control group) and then divided by .9 (assuming a 90% retention rate)

Appendix B: Recruitment Flyer

Do **Vitamin D**
you
have **deficiency?**

You could participate in a research study!

What:

Comparing treatment of Vitamin D deficiency with standard replacement versus single large dose of Vitamin D

Ask your PCP about participating if:

1. You are 18-75 years old
2. Have low Vitamin D
 - a. Less than 20ng/mL

Or contact the Parkview Adult Medicine Clinic to get in touch with [name]

[name] — — — [name]

Appendix C: Screening Questionnaire

Treatment of Vitamin D deficiency with large bolus cholecalciferol in the outpatient setting

Screening Questionnaire

Participant #:

--	--	--

Participant initials:

--	--	--

Demographics:

Sex:

Male Female

Age: _____

Race: Caucasian Hispanic African American Asian Native American Other

Screening questions:

Do you speak conversational English? Y N

Who is your PCP? _____

Are you currently taking Vitamin D? Y N

 If so, how much? _____

 If so, ergocalciferol or cholecalciferol? _____

Are you pregnant or breast feeding? Y N

Do you have a history of:

- | | | |
|---|---|---|
| 1. hypercalcemia (high calcium level) | Y | N |
| 2. hyperparathyroidism (high PTH level) | Y | N |
| 3. CKD w/ baseline Cr >1.1mg/dL | Y | N |
| 4. previous intestinal surgery | Y | N |
| 5. Celiac disease | Y | N |
| 6. Crohn's disease | Y | N |
| 7. ulcerative colitis | Y | N |
| 8. Paget's disease or other bone disorder | Y | N |
| 9. osteoporosis | Y | N |
| 10. granulomatous conditions | Y | N |
| 11. thyrotoxicosis (high thyroid levels) | Y | N |
| 12. active cancer or current chemotherapy treatment | Y | N |

Date _____

Investigator Initials _____

Appendix D: Data collection sheet for initial visit

Treatment of Vitamin D deficiency with large bolus cholecalciferol in the outpatient setting

Screening visit data collection:

Participant #:

--	--	--

Participant initials:

--	--	--

Prescreening 25(OH)D level (ng/mL): _____

Vital signs:

Reading One

Reading Two

Time _____

Time _____

Height: _____

Weight: _____

BMI (calculated): _____

Temperature: _____

Heart rate: _____

Blood pressure: _____

Respiratory rate: _____

Fitzpatrick skin type: I II III IV V VI

Appendix E: Follow-up Questionnaire

Treatment of Vitamin D deficiency with large bolus cholecalciferol in the outpatient setting

Follow-up Visit:

Participant #:

--	--	--

Participant initials:

--	--	--

Visit: 1wk 3mo 6mo 9mo 12mo

Vital signs:

Reading One

Reading Two

Time _____

Time _____

Height:

Weight:

BMI (calculated):

Temperature:

Heart rate:

Blood pressure:

Respiratory rate:

Number of missed vitamin D doses since last visit:

Adverse Events: _____

Adverse Reactions: _____

Initials _____

